2 INTRODUCTION

2.1 Trial Rationale

VTP-850 is a prime-boost immunotherapeutic regimen consisting of 2 viral vectored components, ChAdOx1-PCAQ and MVA-PCAQ. ChAdOx1-PCAQ, the prime dose, consists of a recombinant nonreplicating chimpanzee adenovirus Oxford 1 (ChAdOx1) vector encoding 4 prostate cancer antigens: prostate-specific antigen (PSA), prostatic acid phosphatase (PAP), six-transmembrane epithelial antigen of prostate 1 (STEAP1), and 5T4, an oncofoetal antigen. MVA-PCAQ, the component used for the booster doses, consists of a replication-deficient recombinant Modified Vaccinia virus Ankara (MVA) vector encoding the same prostate cancer antigens as ChAdOx1-PCAQ.

ChAdOx1 and MVA have been incorporated as vectors in different prophylactic vaccines and immunotherapeutics for infectious diseases and cancers. They have both demonstrated immunogenicity in nonclinical and clinical studies for these various indications.

VTP-800 was an earlier immunotherapeutic for prostate cancer that used the same ChAdOx1/MVA heterologous prime/boost platform as VTP-850 but included only one antigen, 5T4. VTP-800 was studied in prostate cancer patients in 2 trials at the University of Oxford.

The VANCE trial in newly diagnosed prostate cancer patients demonstrated immunogenicity and safety of VTP-800. 5T4-specific T cell responses were seen in 25 of the 39 patients (64%), and the median peak for responders was 198 spot forming cells/million.^[1] In the ADVANCE trial in metastatic castration-resistant prostate cancer, VTP-800 was administered with nivolumab, and 5 of 23 patients (22%) had a >50% reduction in PSA level at any time point compared to baseline. Three of the responders had measurable lesions at baseline and also had partial response according to Response Evaluation Criteria in Solid Tumours (RECIST) 1.1. However, 3 of the PSA responses were transient.

Barinthus Biotherapeutics (formerly known as Vaccitech) designed VTP-850 to induce a broader immune response than VTP-800 by encoding multiple antigens to reduce the ability of cancer cells to evade the immune response by mutating or losing expression of any one antigen.

Trial PCA001 is the first-in-human trial of VTP-850. The aim of this trial is to evaluate the safety, immunogenicity, and the rate and duration of PSA response of VTP-850 in patients with biochemical recurrence after definitive local therapy for prostate cancer. The efficacy of VTP-850 will be assessed by the PSA response rate. In addition, the quality of the responses will be characterised by determining the duration of PSA response and by following the responders to establish whether the responders require new treatment for prostate cancer or develop metastases during long term follow-up. During the Dose/Regimen Finding Phase, different dose levels of each component will be evaluated, with the MVA-PCAQ component evaluated in different cohorts as either an intramuscular (IM) injection or an intravenous (IV) infusion.

2.2 Background

Prostate cancer is the second most frequent cancer diagnosis in men and the fifth leading cause of cancer-related deaths in men worldwide.^[2] In 2018, approximately 1.3 million new cases were diagnosed, and approximately 360,000 deaths occurred. The incidence and mortality of prostate cancer increase with age, with the average age of diagnosis being 66 years.^[2] Furthermore, the incidence of prostate cancer is expected to increase due to longer life expectancy and lifestyle factors. The rates are highest in North America, Australia, and northern and central Europe, and lowest in south-eastern and south-central Asia and northern Africa.^[2]

The serum concentration of PSA is usually elevated in men with prostate cancer and is used to monitor the progression of prostate cancer in men who have already been diagnosed with the disease. About 90% of patients with prostate cancer have localised or regional disease at the time of diagnosis. Localised or regional prostate cancer can be treated with radiation or surgical removal of the prostate. These localised therapies can be curative, but the cancer recurs in approximately 20% to 30% of patients. Patients with localised prostate cancer may also receive androgen deprivation therapies (ADTs), as androgens stimulate the growth of prostate cancer cells. Patients with recurrent disease are typically offered ADT when they present with symptomatic local disease progression, proven metastases or a PSA doubling time of less than 3 months.^[3] If a patient has evidence that their cancer is progressing despite ADT, such as increasing PSA in their blood or new bone metastases, it signifies that their disease is castration-resistant.^[4]

Once prostate cancer becomes metastatic, it is considered incurable. Current treatment options for metastatic prostate cancer include androgen receptor inhibitors, such as enzalutamide and abiraterone; chemotherapy including docetaxel and cabazitaxel; a radioactive isotope radium-223; lutetium vipivotide tetraxetan, a radiopharmaceutical, and sipuleucel-T, a patient-specific immunotherapeutic. All of these treatments have been shown to improve survival, but once the cancer is castration-resistant, the median overall survival is less than 3 years.

Recent Phase 3 clinical studies have shown that drugs such as enzalutamide, apalutamide, abiraterone and docetaxel can provide a survival advantage when used earlier in a patient's course of treatment, but the optimal sequence for the different treatment types has yet to be determined.

Patients with prostate cancer have few options once metastatic disease is evident. Targeting the disease earlier in its development may be an effective strategy to prevent or delay the development of metastases and may allow patients to delay or avoid ADT and other therapies. VTP-850 is designed as a potentially low-toxicity immunotherapeutic intervention to treat prostate cancer, prior to metastases forming, while the disease is still considered castration sensitive, but with rising PSA values.

2.3 Benefit/Risk Assessment

More detailed information about the known and expected benefits and risks and reasonably expected adverse events (AEs) of VTP-850 may be found in the Investigator's Brochure (IB).

2.3.1 Risk Assessment

A summary of potential risks for VTP-850 administration is included in [Table 3](#).

Table 3 Summary of Potential Risks for VTP-850 Administration

| Potential Risk of Clinical Significance | Summary of Data/Rationale for Risk | Mitigation Strategy |
|--|---|---|
| Trial Intervention (VTP-850) | | |
| A potential signal of cardiac risk has been identified and assessed following administration of VTP-850 in the trial population | In the first 14 participants treated, a potential cardiac-related death has been reported together with non-serious adverse events of dyspnoea, and dyspnoea exertional and atrial fibrillation in two further participants. These events have a possible temporal relationship to trial intervention, occurring within a similar timeframe after the first MVA-PCAQ boost. | Participants with a history of cardiac events that put them at risk will be excluded from the trial. In addition, cardiac monitoring (ECG and laboratory blood tests) will be performed at pre-defined timepoints during the first 6 months of the trial and a baseline echocardiogram will be performed to exclude participants with any clinically significant abnormalities. |
| Potential for local reactions (injection site redness, injection site swelling and injection site pain) and systemic reactions (including fever, chills, feverishness and headache) following IM administration. | These are common reactions seen with other products that use the same viral vectors as are used in VTP-850. Further details are provided in the current IB. | The investigator site will contact the participant one day after the administration of each component of VTP-850 7 days after the administration of ChAdOx1-PCAQ, and the participant will return to the clinic 7 days after each administration of MVA-PCAQ, at which times the trial staff will record AEs |
| With any immunotherapeutic there is a rare risk of anaphylaxis which can be fatal. | - | Participants will be dosed in a clinical area where appropriate drugs and medical equipment to treat acute anaphylactic reactions are immediately available for the management of such adverse reactions in the immediate post-administration period. Participants are observed in the clinic for at least 30 min post-dose. Participants with history of anaphylaxis to previous vaccination are excluded. |

| Potential Risk of Clinical Significance | Summary of Data/Rationale for Risk | Mitigation Strategy |
|---|--|---|
| Potential risk of elevated liver function tests following IV MVA-PCAQ. | Transient laboratory abnormalities including increases in liver function tests following IV dosing were observed in clinical studies with an MVA-vectorized vaccine for malaria. These abnormalities were without clinical symptoms or signs and returned toward baseline values over time. The clinical significance of these observations is unknown. | Safety labs at 7 and 14 days after each IV administration of MVA-PCAQ. The first 3 participants who receive IV MVA-PCAQ will be staggered so that the second and third participants do not receive MVA-PCAQ until the laboratory results following the previous participant's initial MVA-PCAQ dosing have been assessed. |
| Unknown AEs and laboratory abnormalities with a novel immunotherapeutic. | This trial is the first time VTP-850 will be administered to humans. | Routine safety laboratory testing (including haematology, chemistry, liver function tests) and clinical assessments will be obtained during the Intervention and Follow-up Periods to monitor for expected and unexpected AEs. A Safety Monitoring Committee (SMC) will review safety data during the trial. |
| Potential very rare adverse events that have occurred in people who have received a different ChAdOx1-vectorized product. | There have been very rare events of thrombosis with thrombocytopenia, Guillain Barré Syndrome, and capillary leak syndrome with the ChAdOx1-vectorized vaccine Vaxzevria, which is authorised in many parts of the world. It is not known if these are related to the ChAdOx1 vector. Such events have not been detected with other ChAdOx1-vectorized products to date, and it is not known if they will occur with ChAdOx1-PCAQ. | Participants with previous history of thrombosis with thrombocytopenia, Guillain Barré Syndrome, and capillary leak syndrome have been excluded from the trial because it is possible that they may be at higher risk. |
| Trial Procedures | | |
| Venipuncture will be performed during the trial. | There is the risk of bleeding, bruising, haematoma formation and infection at the venipuncture site. | Only appropriately qualified personnel would perform the blood draw. |

| Potential Risk of Clinical Significance | Summary of Data/Rationale for Risk | Mitigation Strategy |
|---|--|---|
| Bone scans and radiographic assessments will be performed during the trial. | There is a low risk of allergic reaction to contrast material. Bone scans and CT scans involve exposure to small amounts of radiation. | Only appropriately qualified personnel would perform radiographic procedures. |

Abbreviations: AE=adverse event, CT=computed tomography, IM=intramuscular, IV=intravenous

2.3.2 Benefit Assessment

Potential benefits to individual participants may include:

Receipt of a potentially efficacious immunotherapeutic for prostate cancer. However, as this is an early development trial with no previous efficacy data, there may be no such benefit to trial participants.

The participants will receive additional monitoring of their prostate cancer compared to the standard of care.

- Contributing to research to help others. Participation in this trial may contribute to the development of a treatment for prostate cancer.

2.3.3 Overall Benefit-Risk Conclusion

Taking into account the measures taken to minimise risk to participants participating in this trial, the potential risks identified in association with VTP-850 are justified by the anticipated benefits that may be afforded to participants with prostate cancer.

3 OBJECTIVES AND ENDPOINTS

| Primary Objective | Primary Endpoints |
|--|---|
| To evaluate the safety of VTP-850 prime-boost regimens, with the booster dose administered either IM or IV, and establish an RP2R | 
 Number and proportion of participants with AEs, treatment-related AEs, \geGrade 3 AEs, \geGrade 3 treatment-related AEs, serious adverse events, and treatment-related serious adverse events Number and proportion of participants with clinically significant laboratory values Change from baseline for laboratory tests and vital sign measurements at each time point of collection |
| Secondary Objectives | Secondary Endpoints |
| To evaluate the PSA response rate to VTP-850 | 
 Percentage of participants with \ge50% reduction in serum PSA compared to baseline at any time, based on two consecutive measurements, at least 2 weeks apart |
| To evaluate the durable PSA response rate to VTP-850 | 
 Percentage of participants with confirmed PSA response compared to baseline without having PSA progression on or before Month 8. |
| To evaluate the duration of PSA response to VTP-850 (for the subset of participants with PSA response) | 
 Duration of PSA response (for the subset of participants with PSA response), defined as time from date of first dose of VTP-850 to the date of PSA progression (i.e., an increase of \ge25% and an absolute increase of 0.2 ng/mL or more from nadir) |
| To assess the Metastasis-free Survival (MFS) and Time to Metastases (TTM) of the subset of participants with PSA response | 
 MFS is defined as the time from date of first dose of VTP-850 until metastatic disease by conventional imaging (CT/MRI and/or technetium-99 bone scan) or death from any cause, whichever occurs first TTM is defined as the time from date of first dose of VTP-850 until metastatic disease by conventional imaging (CT/MRI and/or technetium-99 bone scan) 
Note that MFS and TTM events do not include local progression events, e.g., progression in pelvic lymph nodes below the aortic bifurcation.
 |
| To assess the time to start of ADT for the participants with PSA response | 
 Time from date of first dose of VTP-850 to the earliest of the start of ADT or the date when criteria to start ADT are met |
| Exploratory Objectives | Exploratory Endpoints |
| To characterise immunogenicity (including antigen-specific T cell magnitude, phenotype and functionality associated with each regimen) | 
CD4+ and CD8+ T cell response to the VTP-850 antigens in the peripheral blood as measured by multi-parameter flow cytometry and enzyme linked immunospot assays
 
 Other immune responses to VTP-850 |

| | |
|--|--|
| To explore association of PSA response with biomarkers | Microsatellite instability-high status (MSI-H), Breast Cancer gene (BRCA) mutations and other molecular markers Expression level of the VTP-850 antigens (PSA, prostatic acid phosphatase [PAP], six-transmembrane epithelial antigen of prostate 1 [STEAP1], 5T4) in historic tumour samples 
 • Circulating tumour DNA • Serum PSA-binding antibodies |
| To look for evidence of resolution of lesions on PSMA scan after administration of VTP-850 (if documented at baseline), and association of resolution of such lesions with PSA response in the subset of participants with baseline PSMA scan who have a PSA response on trial | 
 • PSMA scans (optional) |
| To assess the MFS and TTM of all participants | 
 • MFS is defined as the time from date of first dose of VTP-850 until metastatic disease by conventional imaging (CT/MRI and/or technetium-99 bone scan) or death from any cause, whichever occurs first • TTM is defined as the time from date of first dose of VTP-850 until metastatic disease by conventional imaging (CT/MRI and/or technetium-99 bone scan) Note that MFS and TTM events do not include local progression events, e.g., progression in pelvic lymph nodes below the aortic bifurcation |

Abbreviations: ADT=androgen deprivation therapy, CT=computed tomography, IM=intramuscular, IV=intravenous, MFS=Metastasis-free Survival, MRI=magnetic resonance imaging, PSA= prostate-specific antigen, PSMA=prostate-specific membrane antigen, RP2R=recommended Phase 2 regimen, TTM=Time to Metastases

4 TRIAL DESIGN

4.1 Overall Trial Design

This is a multicentre, Phase 1/2, open-label clinical trial of the VTP-850 prime-boost immunotherapeutic in men with biochemical recurrence after definitive local therapy for prostate cancer. The trial will be conducted in up to 30 centres worldwide.

Participants in all cohorts will receive the ChAdOx1-PCAQ component on Day 1 (prime) and the MVA-PCAQ component on Days 29 and 57 (boosts). Participants will be followed until the Month 6 Visit or start of new therapy such as ADT or until development of unequivocal metastatic prostate cancer. Participants who have a PSA response will be followed for an additional 18 months, up to 24 months from first dose, or until start of new therapy such as ADT or development of unequivocal metastatic prostate cancer. In the event that a participant experiences a confirmed PSA response but subsequently experiences PSA progression more than 2 months after their final dose of VTP-850, an additional dose of MVA-PCAQ may be offered to the participant.

4.1.1 Phase 1 – Dose/Regimen Finding Phase

Phase 1 will determine the recommended Phase 2 regimen (RP2R; dose level of both ChAdOx1-PCAQ and MVA-PCAQ, and route of administration of MVA-PCAQ) that will be used in Phase 2 and will follow a 3+3 design.

Participants will be dosed according to [Table 1](#) during the Screening and Intervention Periods [Table 5](#). The first 3 participants will be enrolled in Cohort 1. Enrolment of the first 3 participants in each cohort will be staggered by at least 9 days. The medical monitor will review the safety data for the previous participant, at least 7 days after the prime dose and after the first booster dose of VTP-850, before the corresponding dose is administered to the next participant. The safety review will include data from at least 7 days after each ChAdOx1-PCAQ prime dose; at least 7 days after the first booster MVA-PCAQ dose if administered IM; and at least 14 days after the first booster dose of MVA-PCAQ if administered IV. If 1 or more of the 3 participants has a dose limiting toxicity (DLT), 3 additional participants may be enrolled into Cohort 1. If there is no DLT after the first dose of VTP-850 in the first 3 participants, 3 participants will be enrolled into each of Cohorts 2 and 3 concurrently, with the first participants in Cohorts 2 and 3 staggered by at least 9 days to allow for medical review.

If DLT is not seen in more than 1 participant in Cohort 2 after the first dose of VTP-850, then an additional 3 participants will be enrolled into Cohort 2. Safety data for the DLT period following each booster dose will be assessed by the medical monitor prior to the corresponding booster dose being administered to additional participants.

If DLT is not seen after the first dose of VTP-850 in more than 1 participant in Cohort 3, then an additional 3 participants will be enrolled into Cohort 3. Safety data for the DLT period following each booster dose will be assessed by the medical monitor prior to the corresponding booster dose being administered to additional participants.

A total of 6 participants in each of Cohorts 2 and 3 will be dosed with MVA-PCAQ on Day 29 and Day 57. Therefore, participants who withdraw before dosing, before completion of dosing or who have dose delays will be replaced (unless the reason for not completing dosing per protocol is related to a stopping rule criteria being met).

If the safety of one or more cohorts is acceptable after all participants have been followed through the DLT period after the first booster dose of VTP-850, then a Phase 2 dosing regimen will be selected based on safety data, and recruitment to Phase 2 will be opened.

A Safety Monitoring Committee (SMC) consisting of the Medical Monitor, sponsor physician, a prostate cancer physician not participating in the trial, and at least 2 investigators will review cumulative safety data and decide whether to enrol each cohort in Phase 1 and whether to open enrolment in Phase 2, and will also choose the RP2R. The SMC will evaluate all events that meet the DLT criteria, taking into consideration the outcome and recovery time of each event.

The DLT evaluation period ends 7 days after each IM injection and 14 days after each IV injection of MVA-PCAQ.

A DLT is defined as any of the following toxicities that occur during the DLT evaluation period and are considered related to trial intervention (Grading is per CTCAE Version 5.0):

- Grade 4 or fatal AE
- Grade 3 or greater hematologic AE that does not recover to Grade 1 or baseline Grade within 72 hours
- Grade 3 or greater hepatic and renal dysfunction that does not improve to \leq Grade 2 within 7 days

Grade 3 or greater AE affecting heart, lung or Central Nervous System (CNS) of any duration (including encephalopathy as defined by Immune Effector Cell Encephalopathy [ICE] or Immune Effector Cell -Associated Encephalopathy criteria [ICAN])

- Grade 3 or greater cytokine release syndrome (CRS) that does not improve to \leq Grade 2 within 72 hours
- Grade 3 or greater clinical AE other than heart, lung or CNS toxicity, hepatic or renal dysfunctions, not resolving to <Grade 2 within 72 hours

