4.1.2 Phase 2 – Main Phase

Phase 2 of the trial will consist of 2 sequential stages.

In Stage 1 of Phase 2, 19 additional participants will be enrolled at the chosen Phase 2 regimen. If 4 or more of the 25 participants at the RP2R (out of the 19 Phase 2 participants and the 6 Phase 1 participants who received the same dose regimen according to the dosing schedule) have a PSA response, Stage 2 will be opened to enrolment. If 3 or fewer of the 25 participants receiving the RP2R have a PSA response, no further participants will be enrolled. PSA response is defined as $\geq 50\%$ reduction in serum PSA compared to baseline at any time, measured at two consecutive timepoints, at least 2 weeks apart. The decision to open recruitment in Stage 2 will be made by the SMC after reviewing available safety and efficacy data after at least 4 participants have exhibited a PSA response.

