7.2 Participant Discontinuation/Withdrawal from the Trial

A participant may withdraw from the trial at any time at his own request or may be withdrawn at any time at the discretion of the investigator for safety, behavioural, disease-management (for example, in the case of rapid PSA progression, a participant may need to discontinue the trial to consider other treatment options) or compliance reasons.

At the time of discontinuing from the trial, if possible, an End of Trial visit should be conducted, as shown in the SoA ([Section 1.3](#)).

The participant will be permanently discontinued from the trial intervention and the trial at that time.

If the participant withdraws consent for disclosure of future information, the sponsor may retain and continue to use any data collected before such a withdrawal of consent.

If a participant withdraws from the trial, he may request destruction of any samples taken and not tested, and the investigator must document this in the site trial records.

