11.4 Sample Size Determination

A total of approximately 144 participants will be enrolled. A sample size of approximately 125 participants will be eligible for inclusion in the Phase 2 efficacy evaluation.

Twenty-five participants are to be included in the preliminary Stage 1 assessment to expand into Stage 2 of Phase 2 (i.e., the first 19 participants enrolled in Stage 1 and the 6 participants from Phase 1 receiving the RP2R according to the dosing schedule). If the true response rate (where response is defined as $\geq 50\%$ reduction in serum PSA at any 2 consecutive post-baseline timepoints at least 2 weeks apart) associated with VTP-850 administration is $\geq 20\%$, 25 participants will yield a 76.6% chance (i.e., power) of observing 4 or more responders.

One hundred and twenty-five participants (combined Stage 1 enrolment as described above and Stage 2 enrolment in Phase 2) will yield the following 90% and 95% Confidence Intervals (CIs) for the true response rate based on the example observed response rates in Table 6. This Phase 2 sample size has 89.3% power to rule out a null proportion of PSA responders of 10% using a two-sided exact test with a target significance level of 0.05 assuming a true response percentage of 20%. The null hypothesis response rate of 10% will be rejected if at least 20 PSA responders (16%) are observed amongst the 125 participants.

The observed response rate and associated CIs will facilitate decision-making regarding whether to continue the program as well as the appropriate sample size for subsequent trials.

Table 6 Confidence Intervals for True Serum PSA Response Rate Based on Observed Response Rate (n=125)

| Observed Response Rate (%) | 90% Confidence Interval | 95% Confidence Interval |
|----------------------------|-------------------------|-------------------------|
| 0.10 | (0.059, 0.156) | (0.054, 0.166) |
| 0.15 | (0.100, 0.213) | (0.092, 0.225) |
| 0.20 | (0.143, 0.268) | (0.134, 0.281) |
| 0.25 | (0.187, 0.322) | (0.177, 0.335) |
| 0.30 | (0.233, 0.375) | (0.221, 0.388) |

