 - Opening recruitment in Stage 2 of Phase 2, after reviewing available safety and efficacy data after at least 4 PSA responders have been identified
 - Altering the dose/ regimen (e.g., dropping back a dose level or dropping the second booster dose)
 - Pausing or stopping the trial
 - The institution of additional safety measures, if considered to be required

A1.6. DISSEMINATION OF CLINICAL TRIAL DATA

- Barinthus Biotherapeutics will share anonymised trial data on a publicly available database, as per local regulations.

Clinical Trial Reports (CSRs), periodic safety reports, and clinical trial summary reports will be disclosed after review by regulatory authorities. This includes access to Clinical Trial Reports from studies with negative outcomes and from terminated development programs.

A1.7. DATA QUALITY ASSURANCE

All participant data relating to the trial will be recorded on eCRFs unless transmitted to the sponsor or designee electronically (e.g., laboratory data). The investigator is responsible for verifying that data entries are accurate and correct by electronically signing the eCRF.

- Guidance on completion of eCRFs will be provided.

The investigator must permit trial-related monitoring, audits, IRB/IEC review, and regulatory agency inspections and provide direct access to source data documents.

Monitoring details describing strategy, including definition of trial critical data items and processes (e.g., risk-based initiatives in operations and quality such as risk management and mitigation strategies and analytical risk-based monitoring), methods, responsibilities, and requirements, including handling of noncompliance issues and monitoring techniques (central, remote or on-site monitoring) will be described in the monitoring plan.

The sponsor or designee is responsible for the data management of this trial, including quality checking of the data.

- The sponsor assumes accountability for actions delegated to other individuals (e.g., contract research organisations).

Records and documents, including signed ICFs, pertaining to the conduct of this trial must be retained by the investigator for 25 years after trial completion unless local regulations or institutional policies require a longer retention period. No records may be destroyed during the retention period without the written approval of the sponsor. No records may be transferred to another location or party without written notification to the sponsor.

A1.8. SOURCE DOCUMENTS

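### The Stage 1 rule counts only Phase 1 men dosed on schedule, so early leavers drop out of the 25 and the 125, and six such men are not assured for every selectable regimen

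*Protocol*

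**What the plan says.** **Who is replaced.** Protocol 4.1.1 requires six men in each of Cohorts 2 and 3 to receive both boosters on Days 29 and 57. To secure this, "participants who withdraw before dosing, before completion of dosing or who have dose delays will be replaced". The one exception is "unless the reason for not completing dosing per protocol is related to a stopping rule criteria being met". The rules in 4.1.6 are safety events only: a related Grade 4 or 5 event, a related SAE, or death within 30 days of a dose. PSA progression is not among them.

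**Who enters the Stage 1 rule.** Under 4.1.2, "19 additional participants will be enrolled at the chosen Phase 2 regimen". The rule begins "If 4 or more of the 25 participants at the RP2R", and the Phase 1 contribution is "the 6 Phase 1 participants who received the same dose regimen according to the dosing schedule". Sections 11.3 and 11.4 use the same 25, and 11.4 adds 100 Stage 2 men to reach 125.

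**Why a man may leave.** Section 7.2 allows withdrawal for disease management and notes that "in the case of rapid PSA progression, a participant may need to discontinue the trial to consider other treatment options".

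**Stated performance.** For a true rate of 20%, 11.4 says "25 participants will yield a 76.6% chance (i.e., power) of observing 4 or more responders". No condition is attached about how many Phase 1 men are available.

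**Other sets.** The intent-to-treat set (protocol 11.1.2) needs enrolment and one dose. The SAP's Efficacy Evaluable Set (4.4) needs, in addition, a baseline and one later PSA. The SAP covers Phase 1 only and leaves Phase 2 to a later plan, so it does not define the Stage 1 decision set.

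**The concern.** There are two separate gaps.

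First, the six Phase 1 men are selected by completing treatment, while the 19 are counted by enrolment, with no replacement rule stated for them. A man who received the prime, saw his PSA climb and left before the second booster has had treatment and has not responded. He is replaced by someone who completed. Removing such men pushes the observed rate up and makes it easier for an inactive regimen to open a 100-man Stage 2.

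Second, the rule is written as 19 plus 6, but the protocol does not guarantee six for every outcome of Phase 1. Cohort 1 has 3 to 6 men, its expansion is optional and follows a DLT, and 4.1.3 leaves its doses selectable if the higher ones are not acceptable. In Cohorts 2 and 3, a man who stops because a stopping rule was met need not be replaced. Nothing says how the rule works with fewer than six. Three or fewer responders ends enrolment, so a shortfall works against an active regimen.

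**Working it through.** **Inputs.** Pass mark 4 of 25, made up of 6 and 19 (4.1.2). True rate 20%, null rate 10%, final rule at least 20 of 125 (11.4). Cohort 1 size 3 to 6 (Table 5). The documents give no rate of progression-related exits. I assume a share q of dosed Phase 1 men at the selected regimen leave as non-responders and are replaced, with q from 10% to 20%.

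**Step 1: the plan's own figures.** For X binomial(25, 0.20), P(X ≥ 4) = 1 − (0.0038 + 0.0236 + 0.0708 + 0.1358) = 0.766, the stated 76.6%. For 125 men and a cut-off of 20, the upper tail at 10% is 0.0237 and the power at 20% is 0.893, the stated 89.3%. A cut-off of 19 gives an upper tail of 0.0428, so 20 is correct for a two-sided 0.05. The arithmetic is sound; the question is who makes up the denominators.

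**Step 2: tracing one man.** He receives the prime, leaves before Day 57 for PSA progression (7.2), and has met no rule in 4.1.6. Under 4.1.1 he is replaced. He did not receive the regimen on schedule, so under 4.1.2 he is not one of the six. Under 11.1.2 he is in the intent-to-treat set.

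**Step 3: size of the replacement effect.** If the rate in all dosed men is p and those who leave do not respond, the rate in completers is p/(1 − q). The count is then binomial(6, p/(1 − q)) plus binomial(19, p). For one early leaver against six completers, q = 1/7 and the completers' rate at p = 10% is 0.10/(6/7) = 0.1167. Summing over k = 0 to 3 responders among the six:

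P(total ≤ 3) = 0.4751×0.8850 + 0.3765×0.7054 + 0.1243×0.4203 + 0.0219×0.1351 = 0.741, so the pass chance is 0.259.

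The last column uses 119 men in place of 19 and a cut-off of 20.

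| q | Pass chance, true 10% | Pass chance, true 20% | Upper-tail alpha, 20/125 |
|---|---|---|---|
| 0 | 23.6% | 76.6% | 0.0237 |
| 10% | 25.1% | 78.5% | 0.0249 |
| 1/7 | 25.9% | 79.5% | 0.0256 |
| 20% | 27.0% | 80.8% | 0.0265 |

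**Step 4: fewer than six available, pass mark kept at 4.** With j Phase 1 men the total is 19 + j.

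| Phase 1 men | Total | P(X ≥ 4), true 20% | P(X ≥ 4), true 10% |
|---|---|---|---|
| 6 | 25 | 76.6% | 23.6% |
| 5 | 24 | 73.6% | 21.4% |
| 4 | 23 | 70.4% | 19.3% |
| 3 | 22 | 66.8% | 17.2% |

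**The case against.** **The progression scenario is narrow.** Serum PSA is drawn on Day 1, Day 29 and Day 57 (Table 1), so a man leaving before the Day 57 dose has one scheduled post-dose result. Inclusion criteria 4 and 9 require no other prostate cancer therapy or ADT planned for 4 months. This stands: such exits should be few, which is why the effect is put at one or so men.

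**The man is not lost everywhere.** The SAP's Efficacy Evaluable Set keeps him if he has a later PSA, and the SMC reviews all available safety and efficacy data. That is true, but the pass mark itself is still applied without him.

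**Requiring scheduled dosing is a legitimate and objective choice.** A rule that depended on the reason for leaving would be worse in an open-label trial, because the reason is assigned when PSA may be known. I accept this, and the fix does not use exit reasons.

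Two stronger readings are tempting and not supported:

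- *Most replacements are hidden failures.* The synopsis plans about 25 Phase 1 men, and 25 − 12 − 6 = 7 to 25 − 12 − 3 = 10 exceed the cohort places. But 6.12 replaces men delayed by the study pause, who are offered further dosing and can respond. No count of progression exits is given. Leaving out delayed men can also remove responders, so the direction is certain only for men who leave as non-responders.
- *The rule could rest on 19 men.* Appendix 1 (A1.5) lets the SMC recommend "dropping back a dose level or dropping the second booster dose", and 19 men would give 54.5%. But 4.1.1 defines the selected regimen by dose levels and route, 4.1 gives both boosters to all cohorts, and A1.5 lists this power separately from choosing the Phase 2 regimen. A one-booster regimen would probably need an amendment, when the rule could be restated.

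Nor do the documents say the rule would be run on 22. They fix 25 and are silent on a shortfall.

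**Conclusion.** Both gaps follow from the text, and both are modest.

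The replacement rule biases the Stage 1 decision upward when the man replaced is a non-responder. At a true 10% rate, the increase in pass chance is about 2 percentage points for one early leaver, and 1.5 to 3.4 points over the assumed 10% to 20% range. The final 20-of-125 rule is barely affected: its upper tail stays below 0.027. These figures assume that early leavers never respond and that only the six Phase 1 men are selected in this way.

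The shortfall needs no assumed exit rate. It arises only if Cohort 1 is selected with fewer than six men, or if the stopping-rule exception leaves Cohort 2 or 3 short. Since 4.1.3 prefers the higher doses and the IV route when safety is acceptable, Cohort 1 is a fallback. If it is used with three men and 19 are added, power at 20% falls by about 10 points, from 76.6% to 66.8%.

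The stated 76.6% and 89.3% are correct for denominators of 25 and 125. What is missing is a rule that delivers those denominators with all treated men in them.

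**What to change.** In protocol 4.1.2, 11.3 and 11.4, with matching text in the Phase 2 SAP:

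1. Define the Stage 1 set and the 125 as all participants who received at least one dose at the selected regimen, counted as non-responders unless a PSA response is confirmed. Allow one exclusion, listed in advance and free of judgement: men whose dosing was delayed by the study pause (6.12).
2. Replace the fixed 19 by 25 minus the number of Phase 1 men so counted. Seven counted men would mean 18 new ones, and three would mean 22. Otherwise, restate the pass probability for the actual number.

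Replacement for the Phase 1 safety assessment stays as it is.

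**Cost.** This is a wording change, and the SAP states that Phase 2 has not started. The Stage 1 total stays at 25, though a selected Cohort 1 of three would need three more Stage 1 men. The observed rate and pass chance become slightly less favourable. If 20% is the rate in completers, the pass chance is 73.6% with one early leaver among the 25 (24 men who can respond) and 70.4% with two (23 men). If 20% is the rate in all dosed men, it stays at 76.6%. The later SAP should say which rate is meant.
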